# C. DEVICE USE AND TRAINING

#### **Instructions for Use**

A description of the neoClose® system and its components, intended use, technical details, warnings, precautions, and procedural steps will be provided to all users in the Instructions for Use. To operate the system, the operator must read the IFU and be fully trained and acquainted with the operation and function of each part of the system. To demonstrate the ease of product utilization, no prior large animal training will be required.

# **D. STUDY OBJECTIVES**

# **Primary Outcome Measure**

To compare technical effectiveness of neoClose® device versus classic Carter- Thomason® suture passer. This will completed by comparing:

- Time required to complete port closure.
- Number of sutures required to complete port closure.
- Time needle is within abdominal cavity.
- Depth of needle into the abdominal cavity.
- Evaluation of surgical site occurrences.
- Evaluation of trocar site hernia incidence with abdominal ultrasound.

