# SYNOPSIS

Study Title	Randomized Trial Evaluating Effectiveness of neoClose ® Abdominal Closure Device versus CarterThomason ® Needle Passer
Trial Design	A randomized trial intended to compare neoClose ® abdominal closure versus standard Carter- Thomason ® closure in a bariatric surgery gastric bypass and sleeve gastrectomy population. The primary objective of the study is to compare the technical effectiveness of the devices. A secondary outcome will be analysis of pain scores associated with the distinct closures.
	The study will be by a group of 6 Bariatric / General Surgeons at a high volume academic institution. Patients will be randomized upon induction of anesthesia and blinded to the closure technique performed. Video analysis of technical effectiveness will be performed as well as clinic follow up at 1 week ,6 weeks and 1 year after the procedure to assess pain scores. In addition, an abdominal ultrasound will be completed at 6 weeks and 1 year to evaluate the incidence of port site hernia.
Procedure	Both devices will be used to close 12 mm camera and stapler port sites upon completion of a robotic assisted laparoscopic gastric bypass and sleeve gastrectomy. The procedure requires a 12 mm port be placed in the midline approximately 3 cm cephalad to the umbilicus and a second in the right mid abdomen. Port sites will be closed as defined as the inability to palpate a fascial defect .

Study Population	Adults aged 18-70 years with BMI > 35 that have completed a multimodality bariatric workup (EGD, nutrition evaluation and psychological evaluation) and selected to have an elective gastric bypass and sleeve gastrectomy. Subjects who fail to complete extensive pre-operative work up including endoscopic surveillance, nutrition visit, psychological clearance will be excluded from the study. A pregnancy test will be done on female subjects as part of Standard of care. There will be 35 patients per group. A power analysis was completed using the data derived from our preclinical porcine study using primary endpoint of time (32 seconds for Carter- Thomason® and 18.5 seconds for neoClose®). The alpha utilized was 0.05. A total of 70 patients will be screened for the study.

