Assessments	
 
The study will allow for the evaluation of technical effectiveness and analysis of pain scoring:
 
Technical Effectiveness 
 
Number of sutures required to complete closure.
 
Time required to complete closure.
 
Depth of needle penetration to complete closure.
 
Evaluate for surgical site occurrences immediately post op as well as at 1 ,6 weeks and 1 year after closure procdure.
 
Evaluation for port site hernia at 6 weeks with abdominal ultrasound.
 
 
 
Pain Evaluation 
 
Visual analog pain scale will be used to assess pain at both port sites.
 
Amount of intravenous narcotics required during hospitalization.
 
Hospital stay duration.
 
 
 
The study will allow for assessment of pain scores during hospitalization and at follow up visits approximately 1 week ,6 weeks and 1 year.
 

Data Collection	During the procedure, an independent examiner will record the amount of time and number of suture passes to obtain port site closure. In addition, an independent review of video from each procedure will be completed to record the time and depth of needle exposure. Patients will fill out pain analog scores

	during hospital stay and follow up visits. Care givers on the floor and in clinic will
	be blinded to the closure technique.
	Hospital records will be reviewed to record narcotic requirements.

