#### **Sleeve Gastrectomy**

Patients having robotic assited sleeve gasterectomy will also be in the study. For this procedure, the same number of trocers and same locations will utilized. The stomach is visualized and fully mobilized. Sleeve gastrectomy is achieved with a linear stapler. The stomach is removed from the 15- mm port site in the right upper quadrant. Similar to the gastric bypass study patients, local anesthesia will not be used to avoid compounding variable in pain assessment.

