#### **Data Collection**

An autonomous recorder will document the number of sutures required to close each port site as well as the time required to obtain closure during the procedure. A video will be created of each procedure followed by careful analysis of the film by an independent reviewer to record the time of needle exposure to the abdominal cavity as well as depth of needle passage.

Each patient will be placed upon a Dilaudid pain pump immediately after the procedure and transitioned to oral narcotics upon initiation of liquid diet. Analog pain scoring will be completed on each hospital day as well as clinic visits approximately 1,6 weeks and 1 year after the operation. In addition, after patient discharge, the amount of narcotics required during hospitalization will be recorded. An abdominal ultrasound will be completed at 6 weeks and 1 year after the operation to evaluate the incidence of trocar site hernias.

The data will be stored on a password protected UT supplied computer in Excel files by MRN and without names. Upon analysis of the data, the MRN will be deleted thereby erasing all potential patient identifiers.

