#### **Data Analysis**

Data will be analyzed using a simple T test within the Excel program as there will be only two groups with a single variable between them. Post Hoc analysis will not be required as with ANOVA secondary to the lack of a third group.

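### Six unranked measures share the primary outcome, but the sample size rests on a single time endpoint that Section D does not name as primary

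*Combined protocol and SAP*

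**What the plan says.** Section D, Primary Outcome Measure, states the objective as technical effectiveness and continues "This will completed by comparing". It then lists six items: closure time ("Time required to complete port closure"), number of sutures, time the needle is in the abdominal cavity, needle depth, surgical site occurrences, and trocar site hernia on ultrasound. None is marked as the main one.

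The Synopsis (Trial Design) gives the same primary objective. Under Study Population, however, it describes a power analysis "using primary endpoint of time (32 seconds for Carter- Thomason® and 18.5 seconds for neoClose", with alpha 0.05 and 35 patients per group. It does not say which time this is, whether it is per port or per patient, or whether alpha is one- or two-sided.

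The Technical Effectiveness list in the Synopsis has one time item, "Time required to complete closure".

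Section B, Data Analysis, is the whole analysis plan: a simple t test for the data. On multiplicity it says only "Post Hoc analysis will not be required as with ANOVA secondary to the lack of a third group".

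**The concern.** A trial that tests at alpha 0.05 needs to say which result answers its primary question. Here the Synopsis points to one endpoint and Section D to six, and the t test comes with no adjustment. The Data Analysis sentence about a third group does not help: it concerns the number of arms, whereas the multiplicity here comes from the number of outcomes.

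The choice of which measure carries the primary conclusion could therefore be made after the data are seen. A mixed result, such as faster closure with deeper needle passage, has no defined reading. Closure time as the powered endpoint is an inference that the text does not confirm.

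**Working it through.** **1. The plan's own figure.** The Synopsis means differ by 32 − 18.5 = 13.5 s. The standard deviation and the power are not stated, so 35 per group cannot be reproduced. It can only be inverted:

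SD = 13.5 / [(z for alpha + z for power) × √(2/35)]

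- Two-sided 0.05, 80% power: 13.5 / [(1.960 + 0.842) × 0.239] = 20.2 s.
- Two-sided 0.05, 90% power: 13.5 / [(1.960 + 1.282) × 0.239] = 17.4 s.

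These show that 35 per group is compatible with one time endpoint tested at an undivided 0.05. They do not identify the time. No alpha is reserved for the other five measures.

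**2. Which time?** Three features of the documents favour closure time:
- It comes first in the Section D list.
- It is the only time in the Synopsis list of technical effectiveness items.
- It is what is recorded during the operation (Section B, Data Collection: "number of sutures required to close each port site as well as the time required to obtain closure"). Needle time is read later from video.

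Against this, needle time is a listed primary measure too, and no section ties 32 s and 18.5 s to either. The unit is also open: the Synopsis says "Both devices will be used to close 12 mm camera and stapler port sites", so each patient has two such sites, while the Appendix 1 day-1 form has one closure-duration entry.

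**3. False-positive chance if any one measure suffices.** Assumptions, none stated in the documents: each measure is tested once, two-sided at 0.05; one significant result counts as meeting the primary objective; the devices do not differ on any measure.

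Six independent tests: 1 − 0.95^6 = 0.265. Four independent tests (the measures other than site occurrences and hernia): 1 − 0.95^4 = 0.185. With equal correlation ρ between normal test statistics, by numerical integration:

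| ρ | six measures | four non-event measures |
|---|---|---|
| 0 | 0.265 | 0.185 |
| 0.3 | 0.241 | 0.174 |
| 0.5 | 0.207 | 0.156 |
| 0.7 | 0.164 | 0.130 |

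**4. Allowing for rare events.** A t test on 0/1 data with few events rarely reaches significance. Its exact size with 35 per arm is 0.0006 at an assumed event rate of 1% in both arms and 0.0051 at 2%. Adding two such event measures, taken as independent of the other four and of each other:

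1 − (1 − four-measure figure) × (1 − size)²

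- Low end (ρ = 0.7, 1%): 1 − 0.870 × 0.9994² = 0.131.
- High end (ρ = 0, 2%): 1 − 0.8145 × 0.9949² = 0.194.

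Across steps 3 and 4 the range is about 13% to 26%, against 5% for one named endpoint.

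**The case against.** The strongest reply is that this is incomplete drafting and not a contradiction. Both sections give technical effectiveness as the objective, powering a trial on one component of a broader objective is common, and the Synopsis does label time as the primary endpoint. It adds that the aim is to compare the devices, so no win need be declared.

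Much of this stands. The objectives do agree, and closure time is clearly the likelier reading, so it would be too strong to infer that the powered time is anyone's guess. What remains is that Section D makes all six measures primary, nothing calls five of them descriptive, and the plan sets an alpha and a test.

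Two other inferences go too far. A reader might take 26% as the expected error rate. It is the upper end, under independence, and even the lower figures depend on an any-one rule that the documents do not state. A reader might also infer that all six measures must succeed, so that hernia alone could block the primary objective. Nothing in the documents sets such a rule, and they give no hernia rates from which to size its effect.

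It is also fair to say that a fixed testing order or a split of alpha would cure the defect. Needle time and depth bear on the visceral and vascular injury named in the Rationale, so making them secondary has a price. A sole primary outcome is preferred here because it carries the Synopsis's own designation into Section D and leaves alpha as it was used for sizing.

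**Conclusion.** The point holds and should be fixed before analysis. One powered endpoint stands against six unranked primary measures, all covered by an unadjusted t test. That finding rests on the text alone and needs no assumption.

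The size does rest on assumptions. If any one significant measure counted as meeting the primary objective, the false-positive chance would be about 13% to 26%, depending on the correlation between measures and on how rare hernia and site events are. The calculation takes two-sided tests, one test per measure and, for the event measures, 35 per arm as in the Synopsis.

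Closure time is probably the powered endpoint, but the sponsor has to confirm it.

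**What to change.** - **Section D, Primary Outcome Measure:** name the time used in the power analysis as the sole primary outcome (closure time, once the sponsor confirms that 32 s and 18.5 s measured it). Use one value per patient, the mean over the two 12 mm ports. Make the other five measures secondary, reported with estimates and 95% confidence intervals and no confirmatory claim.
- **Synopsis, Study Population:** name that same time and state whether alpha 0.05 is one- or two-sided.
- **Section B, Data Analysis:** limit the t test to the primary time and the other continuous measures. Specify risk differences with score-based intervals for site occurrences and hernia. Replace the third-group sentence with this hierarchy.
- **Appendix 1, day-1 form:** record closure duration separately for each port.

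The cost is wording in three sections, an extra line on one form, and a check of what the porcine study timed. No patients or visits are added. The sponsor gives up primary claims on the other five measures, including needle time and needle depth.

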# **Secondary Outcome Measures**

- Comparison of perioperative and post operative pain via visual analog scoring while in the hospital and at follow up appointments 2,6 weeks and 1 year after discharge.
- Comparison of narcotic requirements during hospitalization.
- Comparison of hospital stay duration.

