#### **B. STUDY DESIGN AND PROCEDURE**

#### **Patient Allocation**

This is a randomized study consisting of 35 patients. This site will be the only site across the US doing the study. On the morning of the procedure, qualified subjects who were consented for the study will be randomized to fascial closure with either the neoClose® device or a Carter-

Thomason® suture passer. The floor team and the subjects will be blinded to the closure technique.

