# Follow-up Visit Data Form

Study ID:	Date:
Date of Surgery:	Follow up visit no. :

Pain Medication and dosage:\_\_\_\_\_ Pain Evaluation:

\_

	1 2 L I	3	4	5 	6 	7	8 	9	10 worst
no pain									possible pain

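### No pre-operative pain score or analgesic record is planned, so chance imbalance in prior pain or opioid use can be neither checked nor adjusted for in the pain and in-hospital narcotic comparisons

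*Combined protocol and SAP*

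**What the plan says.** **Outcomes.** Secondary Outcome Measures lists "Comparison of perioperative and post operative pain via visual analog scoring while in the hospital and at follow up appointments", the latter at 2 weeks, 6 weeks and 1 year, and, separately, "Comparison of narcotic requirements during hospitalization". The narcotic comparison therefore stops at discharge; only pain runs to 1 year.

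**Timing of data.** Under Data Collection, "Analog pain scoring will be completed on each hospital day as well as clinic visits approximately 1,6 weeks and 1 year after the operation". For narcotics, "after patient discharge, the amount of narcotics required during hospitalization will be recorded". The record begins after the operation: "Each patient will be placed upon a Dilaudid pain pump immediately after the procedure". (The first clinic visit is at about 1 week here and at 2 weeks under Secondary Outcome Measures. That is a separate inconsistency and does not affect this point.)

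**Forms.** Appendix 1 holds two forms. One is for post-operative day 1, with a field for in-hospital pain medication. The other is for follow-up visits ("Date of Surgery: Follow up visit no"), with a pain medication and dosage field and a 0-10 pain scale. There is no pre-operative form.

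**Eligibility.** The Synopsis and Patient Population set age, BMI, completed work-up, no previous midline laparotomy and a first gastric operation. Neither mentions chronic pain or regular opioid use.

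**Analysis.** Data Analysis specifies a simple t test in Excel with no covariates.

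**Randomization.** Patient Allocation states: "On the morning of the procedure, qualified subjects who were consented for the study will be randomized". Patients and floor staff are blinded to the closure technique.

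**The concern.** Pain relief is one of the reasons the Rationale gives for the new device, and the protocol withholds local anesthetic so that it does not disturb the pain scores. Two other likely influences on pain and narcotic use are left unmeasured: pain the patient already had, and opioids the patient already took. A regular opioid user may need much more narcotic in hospital whichever device is used. With 35 per arm, a few such patients falling mostly on one side can shift that arm's mean.

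The Data Analysis section justifies the t test on the ground that only one variable differs between the groups. For prior pain and opioid use, the planned data give no way to check that. Two of the three secondary outcomes are affected, and a pain score not taken before surgery cannot be taken prospectively afterwards.

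**Working it through.** **Is there a baseline anywhere?** The word perioperative under Secondary Outcome Measures could suggest one. It is not defined, and it is tied to scoring in hospital and at follow-up. The Data Collection schedule and both forms in Appendix 1 contain only post-operative entries. No baseline is planned.

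**The plan's own figure.** The only sample-size figure is 35 per group, based on closure time (32 s against 18.5 s, alpha 0.05). No SD, power or sidedness is given, so it cannot be reproduced. It concerns closure time and says nothing about pain or narcotics. I take 35 per arm from the Synopsis; Patient Allocation gives 35 patients for the study, which is a separate inconsistency.

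**Does the missing baseline bias the t test?** In 40,000 simulated trials of 35 per arm with no device effect and an assumed baseline-to-outcome correlation of 0.5, the unadjusted t test rejected in 5.1% of trials and the mean difference was about 0. So there is no bias.

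**How much precision is lost?** The documents give no correlation r, so r is assumed. Adjustment multiplies the residual variance by 1 − r² and the standard error by √(1 − r²). The smallest detectable difference (two-sided 0.05, 80% power, normal approximation) is (1.96 + 0.84) × √(1 − r²) × √(2/35), in SD units.

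| Assumed r | Variance factor | SE factor | SE reduction | Detectable difference | Power for 0.5 SD |
|---|---|---|---|---|---|
| 0 (no adjustment) | 1.00 | 1.000 | – | 0.67 SD | 55% |
| 0.2 | 0.96 | 0.980 | 2% | 0.66 SD | 57% |
| 0.3 | 0.91 | 0.954 | 5% | 0.64 SD | 59% |
| 0.5 | 0.75 | 0.866 | 13% | 0.58 SD | 68% |

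**How likely is a chance imbalance?** For a continuous baseline, the difference between arm means has standard error √(2/35) = 0.24 SD, so a gap above 0.25 SD arises in about 30% of trials. For regular opioid use, two independent binomial arms of 35 give:

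| Assumed rate of regular use | Gap of 3 or more users | Gap of 4 or more users |
|---|---|---|
| 5% | 16% | 5% |
| 10% | 31% | 16% |
| 20% | 45% | 29% |

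**What could an imbalance do to the narcotic means?** As an illustration, suppose regular users need 4 times the usual amount and the arms hold 4 and 1 such patients.
- Means: (31 × 1 + 4 × 4)/35 = 47/35 = 1.34 and (34 × 1 + 1 × 4)/35 = 38/35 = 1.09. The ratio is 1.24, with no device effect.
- Would it reach significance? With no other variation, the arm variances are 0.938 and 0.257. SE = √(1.195/35) = 0.185 and t = 0.257/0.185 = 1.39, p about 0.17. Ordinary variation between patients would lower the expected t further.

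So an imbalance of this kind can distort the estimate noticeably, but this example would not produce a false-positive test.

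**The case against.** Two stronger readings are tempting. The first is that pre-existing pain or opioid use cannot be told apart from the effect of closure. The documents do not support this for the comparison between arms. Patients are randomized and blinded, prior pain and opioid use fall equally on both arms in expectation, and the t test keeps its error rate. In a single patient, late pain cannot be assigned to the port closure without a baseline, but the trial compares arms.

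The second is that narcotic use is also compared out to 1 year. It is not. The follow-up form collects pain medication, but no comparison of it is listed.

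Other objections have weight:

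- The Synopsis says pain is scored at both port sites. Those sites do not exist before surgery, so a pre-operative score there should be near zero, and a high correlation with later pain is unlikely. This largely stands. It is softened because the forms carry one scale with no site marked, so other abdominal pain can enter the recorded score.
- Opioid history might be recoverable later, since hospital records are reviewed and every patient has an extensive work-up. The documents do not say whether the work-up records regular opioid use, so neither recovery nor loss is shown.
- With very few opioid users per arm, the adjustment coefficient would be poorly estimated. This is fair; the tabulation by arm would still be informative.
- These are secondary outcomes, and the multiplier, rates and correlations are all assumed. That is correct, and it limits the weight of the point.

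**Conclusion.** The point holds as a minor one. The plan records neither pain nor regular analgesic or opioid use before surgery, does not exclude patients on either ground, and makes no provision for adjustment. The consequence is not bias. It is an imbalance that can be neither checked nor corrected in the in-hospital narcotic comparison and in the pain comparison to 1 year, together with a modest loss of precision.

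The case is stronger for narcotic use than for pain. The sizes rest on assumed correlations and assumed rates of opioid use, and on 35 patients per arm. If few patients use opioids and nearly all score 0 before surgery, the practical loss is small.

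**What to change.** 1. On the morning of surgery, before randomization, have each consented patient complete the existing Follow-up Visit Data Form once, labelled visit 0: the 0-10 pain score, and regular analgesic or opioid use (yes/no, with drug). The Synopsis places randomization at induction of anesthesia and Patient Allocation places it on the morning of the procedure. Either way, the form must be done while the patient is awake and unallocated.
2. State which region the score refers to, in the same words at visit 0 and at later visits.
3. Tabulate both items by arm.
4. In Data Analysis, prespecify that in-hospital narcotic use is compared with adjustment for pre-operative opioid use, and pain with adjustment for the visit 0 score, by ANCOVA or linear regression in place of the simple t test.

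Cost: about a minute per patient, with no extra visit or procedure, and an analysis slightly beyond a simple t test. The gain will be little if nearly all patients score 0 and few use opioids.
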